### **9.4. Statistical Analyses**

The Statistical Analysis Plan will be finalized prior to interim DBL and it will include a more technical and detailed description of the statistical analyses described in this section. This section is a summary of the planned statistical analyses of the most important endpoints including primary and key secondary endpoints.

#### **9.4.1. General Considerations**

Analysis populations are defined in Section 9.3, Populations for Analysis Sets. Planned analyses are defined in Section 9.5, Planned Analysis.

For safety and immunogenicity analyses, results will be analyzed by vaccine group. In addition, safety and immunogenicity analyses will be repeated by vaccine group and participant seropositivity status at screening. Immunogenicity subanalyses will also be performed by BMI, ethnicity, and other factors as will be described in the Statistical Analysis Plan.

#### **9.4.2. Primary Endpoints**

##### **Safety Endpoints**

No formal statistical testing of safety data is planned. Safety data will be analyzed descriptively by vaccine group. In addition, for selected tables, tabulations pooled by vaccine dose will also be provided. All safety analyses will be made on the FAS.

---

a If a participant would be vaccinated out of window due to a study pause (per Section 6.9), this will not by default be a reason for excluding this participant from the PPI. A sensitivity analysis might also be performed. Further details will be described in the Statistical Analysis Plan.

## **Adverse Events**

The verbatim terms used in the eCRF by investigators to identify AEs will be coded using the Medical Dictionary for Regulatory Activities (MedDRA). All reported AEs will be included in the analysis. (S)AEs caused by molecularly confirmed SARS-CoV-2 infection will be removed at the analysis level from the (S)AE listings and tables and presented separately. For each AE, the percentage of participants who experience at least 1 occurrence of the given event will be summarized by vaccine group.

Summaries, listings, datasets, or participant narratives may be provided, as appropriate, for those participants who die, who discontinue vaccine due to an AE, or who experience a severe AE, an AESI, or an SAE.

Solicited local (at injection site) and systemic AEs will be summarized descriptively. The number and percentages of participants with at least one solicited local (at injection site) or systemic AE will be presented. The frequencies by vaccine group as well as frequencies according to severity and duration will be described for solicited AEs. Frequencies of unsolicited AEs, separately for all and vaccination-related only, will be presented by System Organ Class and preferred term, while those of solicited AEs will be presented only by preferred term.

## **Clinical Laboratory Tests**

Laboratory data (abnormal or graded, when available) will be listed and/or tabulated by participant and time point.

## **Vital Signs**

Vital signs including temperature, pulse/heart rate, respiratory rate, and blood pressure (systolic and diastolic) will be summarized over time, using descriptive statistics and/or graphically. The percentage of participants with values beyond clinically important limits will be summarized.

## **Physical Examinations**

Physical examination findings will be summarized at baseline. A listing of the abnormalities will be made.

### **9.4.3. Secondary Endpoints**

#### **Immunogenicity Endpoints**

No formal hypothesis on immunogenicity will be tested. Descriptive statistics (geometric mean and 95% confidence interval, or median and interquartile range Q1-Q3, as appropriate) will be calculated for continuous immunologic parameters at all available time points. Graphical representations of immunologic parameters will be made as applicable. Frequency tabulations will be calculated for discrete (qualitative) immunologic parameters as applicable.

In addition, the ratio between neutralizing and binding antibodies as determined by VNA and S protein ELISA, respectively, will be calculated.

The immunogenicity analyses will be performed on the PPI population. Immunogenicity analyses will also be done on the FAS (participants who became infected during the study will be analyzed as a subgroup and shown in the graphs using different colors and symbols).

#### **9.4.4. Tertiary/Exploratory Endpoint(s)**

Detailed statistical methodology for analysis of exploratory endpoints will be described in the Statistical Analysis Plan.

#### **9.4.5. Other Analyses**

Descriptive analysis will be performed for the results of the SIC and results of diagnostic tests for SARS-CoV-2 infection after screening. Further details will be provided in the Statistical Analysis Plan.

Statistical analysis of biomarker responses (eg, RNA-seq responses) and LNA immune responses will be detailed in a separate Statistical Analysis Plan.

### **9.5. Planned Analysis**

Interim and primary analyses for each cohort are presented in [Figure 9](#). Additional interim analyses may be conducted by the sponsor as needed.

#### **Interim and Primary Analyses for Cohort 1a**

A first interim analysis post-dose 1 for Cohort 1a is planned when approximately 375 participants have completed Day 29 (ie, 28 days after the first study vaccination) or discontinued the study earlier. This interim analysis will include all available safety data for approximately 375 participants through Day 29 and may include immunogenicity data (VNA, ELISA, and Th1/Th2 assay) for at least 25 seronegative participants (ie, participants who were seronegative at screening) per group through Day 15 (ie, 14 days after the first study vaccination)a. A second interim analysis for Cohort 1a will include immunogenicity data through Day 29 (all available VNA and ELISA data for seronegative participants; Th1/Th2 assay data for approximately 40 seronegative participants per group). For logistical reasons, aspects of the first and second interim analyses may be combined.

The first primary analysis post-dose 2 for Cohort 1a will be performed when approximately 375 participants have completed Day 85 (ie, 28 days after the second study vaccination) or discontinued the study earlier. The primary analysis will include all available safety data for all participants through Day 85. It may also include immunogenicity data through Day 71, ie, 14 days after the second study vaccination (all available VNA and ELISA data for seronegative participants; Th1/Th2 assay data for approximately 40 seronegative participants per group)a. A second primary analysis for Cohort 1a will include immunogenicity data through Day 85 (all available VNA and ELISA data for seronegative participants; Th1/Th2 assay data for

---

a May be performed based on operational availability of data.

approximately 40 seronegative participants per group). For logistical reasons, aspects of the first and second primary analyses may be combined.

### **Interim and Primary Analyses for Cohort 2**

An interim analysis for Cohort 2 will be performed when 28-day safety data is collected for approximately 270 participants after the first study vaccination. This safety analysis may be required as the basis for enrollment of adults aged  $\geq 18$  to  $\leq 55$  years in subsequent larger studies. It will also include available immunogenicity data for seronegative participants (VNA and ELISA).

The primary analysis for Cohort 2 will include all available safety data for approximately 270 participants through 28 days after completion of the second study vaccination in the 2-dose primary regimen. It will also include available immunogenicity data for seronegative participants (VNA and ELISA).

Interim analyses of the data from each booster vaccination will be performed after the last participant receives their respective booster vaccination and will include all available safety and immunogenicity data up to 28 days after the vaccination. These interim analyses will present the data in a group-level unblinded fashion, as follows:

- The interim analysis of the first booster vaccination (at 6 months for Cohort 2a or at 8 months for Cohort 2b), will keep the groups 1, 3, and 4 pooled.
- The interim analysis of the second booster vaccination (at 12 months for Cohort 2a or at 14 months for Cohort 2b), will keep the groups 1 and 4 pooled.

This stepwise group-level unblinding approach avoids indirect unblinding of individual participants who have yet to receive the active (or last) booster (eg, due to rare or unique events).

### **Interim and Primary Analyses for Cohort 3**

The analysis strategy for Cohort 3 is the same as for Cohort 1a.

A first interim analysis post-dose 1 for Cohort 3 is planned when approximately 375 participants have completed Day 29 (ie, 28 days after the first study vaccination) or discontinued the study earlier. This interim analysis will include all available safety data for approximately 375 participants through Day 29 and may include immunogenicity data (VNA, ELISA, and Th1/Th2 assay) for at least 25 seronegative participants per group through Day 15 (ie, 14 days after the first study vaccination)a. A second interim analysis for Cohort 3 will include immunogenicity data through Day 29 (all available VNA and ELISA data for seronegative participants; Th1/Th2 assay data for approximately 40 seronegative participants per group). For logistical reasons, aspects of the first and second interim analyses may be combined.

The first primary analysis post-dose 2 for Cohort 3 will be performed when approximately 375 participants have completed Day 85 (ie, 28 days after the second study vaccination) or

---

a May be performed based on operational availability of data.

discontinued the study earlier. The primary analysis will include all available safety data for all participants through Day 85. It may also include immunogenicity data through Day 71, ie, 14 days after the second study vaccination (all available VNA and ELISA data for seronegative participants; Th1/Th2 assay data for approximately 40 seronegative participants per group)a. A second primary analysis for Cohort 3 will include immunogenicity data through Day 85 (all available VNA and ELISA data for seronegative participants; Th1/Th2 assay data for approximately 40 seronegative participants per group). For logistical reasons, aspects of the first and second primary analyses may be combined.

### **End-of-study Analysis**

The end-of-study analysis will be performed when all included participants have completed the last visit or last booster vaccination follow-up visit or discontinued the study earlier.

### **Planned Analyses: General Considerations**

For all analyses, all data available at the time of the analysis will be included. If any of the above-mentioned analyses coincide, the analyses will be combined. Additional interim analyses may be performed for safety and/or immunogenicity to facilitate decision making with regards to the planning of future studies.

The Statistical Analysis Plan will describe the planned analyses in greater detail.

### **Analysis and Reporting of Unblinded Data**

[figure not shown]
Selected available group unblinded immunogenicity data and blinded safety data from the interim analysis of Cohorts 1a, 1b, and 3 will be published. Following the 7-day post-vaccination 2 safety data being available in Cohorts 1a, 1b, and 3, the sponsor will be unblinded for these cohorts, except for sponsor personnel directly involved with the study site for assessment of safety. Participants, clinical staff, and study-site personnel will remain blinded to the study vaccine allocation.

Selected members of the statistical programming and the statistics group will receive individual level unblinded data pertaining to study VAC31518COV1001 when unblinding at the participant level is required. In addition, they will monitor the number and severity of molecularly confirmed COVID-19 cases in the Ad26.COV2.S and placebo groups to identify an imbalance between groups if it occurs (see Statistical Analysis Plan). They will inform the DRC as soon as an imbalance between groups is detected. A prespecified threshold (imbalance above a certain percentage and/or number of cases) that will trigger notification of the DRC will be described in the Statistical Analysis Plan.

Following Emergency Use Authorization (EUA), conditional licensure, or approval in any country for the single-dose regimen of  $5 \times 10^{10}$  vp Ad26.COV2.S and local approval of protocol Amendment 10 by both Health Authority (HA) and Independent Ethics Committees (IEC)/Institutional Review Board (IRB), a single dose of  $5 \times 10^{10}$  vp Ad26.COV2.S will be offered to enrolled participants who initially received placebo only, resulting in de facto unblinding of

participants and investigators. A stepwise group-level unblinding approach will be used for Cohort 2 to avoid indirect unblinding of individual participants.

**Figure 9: Interim and Primary Analyses**

\*May be performed based on operational availability of data.

\*\*Analysis of VNA/ELISA may be performed before availability of Th1/Th2 data, which may not be available at the time of this analysis.

ELISA = enzyme-linked immunosorbent assay; Th = T-helper; VNA = virus neutralization assay

## **9.6. Analyses for Participants Requesting Unblinding to Receive an Authorized/Licensed COVID-19 Vaccine**

Investigators may receive requests to unblind study participants who become eligible to receive an authorized/licensed COVID-19 vaccine if/when these become available. In these cases, the investigator will discuss with the participant available options and ramifications. If the participant is eligible for an authorized/licensed vaccine according to local immunization guidelines or recommendations and if the participant wishes to proceed with the unblinding, the investigator will follow the unblinding procedures. The reason for the unblinding request should be documented.

When unblinding, if it is determined that the participant received the Ad26.COV2.S vaccine (and not placebo), the participant will be informed that there are no clinical data on the safety of receiving a different COVID-19 vaccine after receiving Ad26.COV2.S. In the event of a participant unblinding to receive an authorized/licensed COVID-19 vaccine and the participant received an authorized/licensed COVID-19 vaccine outside of the study, no further study vaccination will be permitteda. Unblinded participants, whether in the vaccine or control group that did not receive an authorized/licensed COVID-19 vaccine outside of the study, will be asked to continue to be followed in this study in line with the SoA to the extent that they permit, including Cohort 2 booster vaccinations. Safety and immunogenicity evaluations will be identical for all participants, including participants that are unblinded to obtain an authorized/licensed COVID-19 vaccine and who remain in the study, if applicable and feasible.

Procedures installed at the time of unblinding all participants after EUA or approval in any country and local approval of protocol Amendment 10 (refer to Section 8.6), will also apply to participants who were unblinded at their own request prior to Amendment 10. The statistical analyses will follow the same approach as outlined in Section 9.7. The only exception is for Cohorts 2a and 2b participants: if unblinding occurs at their request, they are likely to be completely unblinded, implying they would know in advance whether they would receive active vaccine or placebo at each of the booster time points. These participants will therefore not be included in any of the post-booster safety or efficacy analyses of Cohorts 2a and 2b. If they continue with the booster vaccinations and all study procedures as described in the SoA, they will be included in the immunogenicity analysis.

## **9.7. Analyses after Unblinding all Participants Following EUA or Approval in any Country**

### **9.7.1. Cohorts 1a, 1b, and 3**

The participants in these cohorts have completed the planned study vaccination regimen by the time of unblinding (or have discontinued earlier). In general, after unblinding, participants who received placebo only during primary regimen, can elect to receive a single dose of

a Following local approval of protocol Amendment 15, participants who received an authorized/licensed COVID-19 vaccine outside of the study are allowed to receive a single ad hoc booster dose of Ad26.COV2.S vaccine ( $5 \times 10^{10}$  vp) if the last vaccination was  $\geq 6$  months ago.

$5 \times 10^{10}$  vp Ad26.COV2.S offered at the study site, can opt to receive an authorized/licensed COVID-19 vaccine outside of the study, or may choose not to receive any additional vaccinations. Participants who already received active vaccine will be asked to continue the study or can opt to receive an authorized/licensed COVID-19 vaccine outside of the study.

The safety analyses will be censored at the date of unblinding or the receipt of an unscheduled vaccinea, whichever event occurs first. SAEs and AESIs reported after unblinding or receipt of an unscheduled vaccine, whichever comes first, will be listed.

The immunogenicity analyses will be censored at the date of the receipt of an unscheduled vaccine. Immunogenicity samples taken after the receipt of an unscheduled vaccine will be included in the listings and flagged. Samples obtained from unblinded participants who do not get any further vaccination, will not be censored from the analyses.

Efficacy analyses will be censored at the date of unblinding or the receipt of an unscheduled vaccine, whichever comes first.

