### 3. OBJECTIVES AND ENDPOINTS

A description of study cohorts is provided in Section [4.1](#).

Objectives	Endpoints
Primary 
 
To assess the safety and reactogenicity of Ad26.COV2.S at 2 dose levels, <math>5 \times 10^{10}</math> vp and <math>1 \times 10^{11}</math> vp, administered IM as a single-dose or 2-dose schedule in healthy adults aged <math>\geq 18</math> to <math>\leq 55</math> years and in adults aged <math>\geq 65</math> years in good health with or without stable underlying conditions.
 
	All participants* in Cohorts 1, 2, and 3: 
 
Solicited local and systemic AEs for 7 days after each vaccination in the primary regimen
 
Unsolicited AEs for 28 days after each vaccination in the primary regimen
 
 For the primary endpoint: Serious adverse events (SAEs) and adverse events of special interest (AESIs) from the first vaccination until 2 years after the second vaccination for Cohorts 1 and 3, and until 6 months after the primary regimen for Cohort 2
Secondary 
 
To assess the humoral and cellular immune response to Ad26.COV2.S
 
	Humoral Immune Response All participants* in Cohorts 1, 2, and 3: 
 
SARS-CoV-2 neutralization: SARS-CoV-2 neutralizing titers in serum measured by a virus neutralization assay (VNA [wild-type virus and/or pseudovirion expressing S protein])
 
SARS-CoV-2-binding antibodies measured by enzyme-linked immunosorbent assay (ELISA): Analysis of antibodies binding to the SARS-CoV-2 S protein.
 
 Cellular Immune Response A subset of participants* in Cohorts 1, 2, and 3: 
 
Th1 and Th2 immune responses as assessed by flow cytometry after SARS-CoV-2 S protein peptide stimulation of peripheral blood mononuclear cells (PBMCs) and intracellular staining [ICS] including CD4+/CD8+, IFN<math>\gamma</math>, interleukin [IL] 2, TNF<math>\alpha</math>, IL-4, IL-5, IL-13, and/or other Th1/Th2 markers.
 

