#### **8.3.1. Time Period and Frequency for Collecting Adverse Event, Adverse Events of Special Interest, and Serious Adverse Event Information**

##### **All Adverse Events**

For all cohorts, AEs and special reporting situations, whether serious or non-serious, that are related to study procedures or that are related to non-investigational sponsor products will be reported for all participants from the time a signed and dated ICF is obtained until the end of the study/early withdrawal.

Clinically relevant medical events not meeting the above criteria and occurring between the signing of the ICF and moment of first vaccination will be collected on the Medical History eCRF page as pre-existing conditions.

Solicited AEs, collected through a diary, will be recorded for each vaccination from the time of vaccination until 7 days post-vaccination.

All other unsolicited AEs and special reporting situations, whether serious or non-serious, will be reported for each vaccination from the time of vaccination until 28 days post-vaccination. Unsolicited AEs with the onset date outside the timeframe defined above (>28 days after previous study vaccination), which are ongoing on the day of the subsequent vaccination, should be recorded as such.

All SAEs and AEs leading to discontinuation from the study/vaccination (regardless of the causal relationship) are to be reported for all participants from the moment of first vaccination until completion of the participant's last study-related procedure, which may include contact for safety follow-up. The sponsor will evaluate any safety information that is spontaneously reported by an investigator beyond the time frame specified in the protocol. Suspected AESIs will be reported once local approval of protocol Amendment 11 is obtained until the end of the study/early withdrawal.

All AEs will be followed until resolution or until clinically stable.

As of protocol Amendment 16, for all participants:

- A passive follow-up approach is adopted, defined as on-site study visits to document new COVID-19 events as SAEs or AEs, as applicable. Participants may also contact the site at any time in between scheduled visits to report a safety concern (eg, hospitalization) or COVID-19 episodes.
- Concomitant medications for these events should be reported.
- If a COVID-19 confirmatory laboratory or assay read-out is available, this should be reported in the eCRF together with the method of the test if known.

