### **9.7.2. Cohorts 2a and 2b**

The participants in Cohorts 2a and 2b will not have completed the planned vaccination schedule by the time of unblinding, because the booster vaccinations will not yet have occurred.

For safety, efficacy, and immunogenicity, the same analysis strategy will be applied as for Cohorts 1a, 1b, and 3.

[figure not shown]
Analyses pertaining to the booster vaccinations will be produced as planned. The analyses will include all available participants who have followed the vaccination schedules as per the study design (ie, did not receive an unscheduled vaccination). Note that the post-booster safety or efficacy analyses will not include participants who were unblinded at their own request, since they are likely to be completely unblinded (implying they would know in advance whether they would receive active vaccine or placebo at each of the booster time points). Participants who continue with the booster vaccinations and all study procedures as described in the SoA, will be included in the immunogenicity analysis.

The analysis strategy is depicted graphically in [Figure 10](#).

---

a Unscheduled vaccination: for placebo participants: a single dose of  $5 \times 10^{10}$  vp Ad26.COV2.S offered at the study site or an authorized/licensed COVID-19 vaccine offered outside of the study; for participants in the active vaccine groups: an authorized/licensed COVID-19 vaccine offered outside of the study.

Figure 10: Analysis strategy after unblinding, depicted by scenario

AESI adverse event of special interest; C cohort; SAE serious adverse event

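### The primary SAE/AESI endpoint runs to 2 years (6 months in Cohort 2), but safety analyses are censored at unblinding and later events only listed, so for unblinded participants the defined window has no by-group summary

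*Protocol*

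**What the plan says.** Protocol Section 3 defines the primary SAE and AESI endpoint as running "from the first vaccination until 2 years after the second vaccination for Cohorts 1 and 3". The remaining cohort has a shorter limit, namely "until 6 months after the primary regimen for Cohort 2". A footnote leaves out placebo-only participants who took the crossover dose at unblinding.

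Section 9.4.2 describes the summary: for each event, "the percentage of participants who experience at least 1 occurrence of the given event will be summarized by vaccine group". It also says that every reported AE enters the analysis.

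Section 9.7.1 then limits that analysis: "The safety analyses will be censored at the date of unblinding or the receipt of an unscheduled vaccine", whichever is first. What follows is handled thus: "SAEs and AESIs reported after unblinding or receipt of an unscheduled vaccine, whichever comes first, will be listed". Section 9.7.2 says that for Cohort 2 "the same analysis strategy will be applied as for Cohorts 1a, 1b, and 3". Section 9.8 makes the ad hoc booster a further reason to censor the main analyses.

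Unblinding (Section 8.6) reaches all enrolled participants, active groups included, wherever Amendment 10 is locally approved after authorisation of the single-dose regimen. Section 9.7.2 says Cohort 2 will not have finished its schedule by then "because the booster vaccinations will not yet have occurred".

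On AESI collection, Section 8.3.1 says: "Suspected AESIs will be reported once local approval of protocol Amendment 11 is obtained until the end of the study/early withdrawal". Section 8.3.6.1 adds that the sponsor will try to gather information on thrombotic, thrombocytopenia or TTS events reported before that amendment.

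**The concern.** A primary endpoint needs an analysis over the period that defines it. Here the endpoint asks for SAEs and AESIs over 2 years or 6 months, while the analysis rule stops at an event that, where Amendment 10 applies, comes well before the end of that period. Later events go to a listing, which has no denominator, no group percentage and no follow-up time.

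The AESI component is more exposed than the SAE component. SAEs are collected from first vaccination, so some SAE follow-up is always analysed. AESIs are collected prospectively only from local approval of a later amendment, so much or all of that time may fall after censoring.

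At stake is whether the end-of-study report can state by vaccine group how often SAEs and AESIs occurred over the period that Section 3 names.

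**Working it through.** **Inputs**
- Endpoint limits: Section 3.
- Target days: Schedules of Activities (dose 2 on Day 57; Day 422 and Day 787 visits in Cohorts 1 and 3; 6-month visits on Day 183 in Cohort 2a and Day 239 in Cohort 2b).
- Amendment dates: document history (original 4 May 2020; Amendment 6, 19 September 2020; Amendment 10, 25 February 2021; Amendment 11, 6 May 2021; Amendment 15, 7 October 2021). These are global version dates. Local approval and unblinding dates are not given.

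**Visit days reproduce.** 57 + 365 = 422; 57 + 730 = 787; 1 + 182 = 183; 57 + 182 = 239. The protocol states no figure for follow-up inside the censored analysis, so there is none to reproduce.

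**Cohorts 1 and 3.** Assume the earliest first dose is the original protocol date, 4 May 2020. Dose 2 on target is 56 days later, 29 June 2020, and the 2-year point is 29 June 2022. Analysed follow-up after dose 2 is at most (unblinding date − 29 June 2020):

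| Unblinding on the date of | Days after dose 2 | Share of 730 |
|---|---|---|
| Amendment 10 (25 Feb 2021) | 241 | 33% |
| Amendment 11 (6 May 2021) | 311 | 43% |
| Amendment 15 (7 Oct 2021) | 465 | 64% |

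Taking dose 2 at the early edge of its window (3 days sooner) changes 241 to 244. Later first doses give less. Nobody unblinded in this range reaches 2 years.

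**Cohort 2.** The first booster is due 6 months after the primary regimen, which is where the primary window closes. If unblinding precedes the boosters, as Section 9.7.2 says, the window is still open at censoring, apart from the ±21-day visit allowance. As a check, assume no Cohort 2 dose before Amendment 6. The 6-month target is then no earlier than 19 September 2020 + 182 days = 20 March 2021 (2a), or + 56 + 182 days = 15 May 2021 (2b). Both fall after the Amendment 10 date, by 23 and 79 days. A late local unblinding could let early enrollees complete the window, so the point rests on the protocol's own statement.

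**AESIs.** Amendment 10 to Amendment 11 is 70 days by global date. If a participant was unblinded before local Amendment 11 approval, prospective AESI time inside the censored analysis is zero. If unblinding came later, it is the interval between the two, which the documents do not allow anyone to compute.

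**Does another section supply the missing summary?**
- Section 6.6 says that, after own-request unblinding, data are analysed separately under Sections 6.3 and 9.6. Section 9.6 refers the analysis to 9.7, which gives a listing for later SAEs and AESIs. The promise leads back to the same rule.
- Section 9.8 analyses SAEs and AESIs by original regimen to end of study, but only for ad hoc booster recipients and only from the booster onward.
- The Cohort 2 booster analyses in 9.7.2 go ahead, and Section 3 has an exploratory Cohort 2 SAE/AESI endpoint to end of study. Neither summarises by group the stretch from unblinding to the 6-month visit.
- Active recipients in Cohorts 1 and 3 who decline the ad hoc booster get no by-group SAE/AESI summary after unblinding.

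**The case against.** Censoring at unblinding is openly stated and has a reason: later reporting is open-label, and placebo recipients cross over. The study is descriptive, with no safety hypothesis, and the choice between percentages and person-time rates is ordinary analysis-plan detail. All of that stands. It supports keeping the censored analysis for the blinded comparison, but it does not supply the analysis that the endpoint calls for. The protocol itself accepts descriptive open-label summaries elsewhere: immunogenicity is not censored at unblinding, and ad hoc booster SAEs and AESIs are to be analysed.

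A second argument concerns harm. TTS is the only AESI, and Section 2.3.1 places reported cases within 3 weeks of vaccination. In Cohorts 1 and 3 that period lies before unblinding, inside the 28-day unsolicited AE window and continuous SAE collection, with platelet counts 7 days after each primary dose. This also stands. For those cohorts the early risk period is not lost; what is missing is mainly the AESI designation and enhanced work-up. The endpoint nevertheless runs far beyond 3 weeks.

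Several stronger readings are tempting and are not supported:
- That the endpoint is never analysed. SAEs before unblinding are analysed, later ones are listed, and booster recipients are analysed to end of study.
- That AESI collection starts only after the analysed period ends. Both triggers are local events without dates, and Section 8.3.6.1 seeks earlier events retrospectively.
- That truncated results would be presented as 2-year or 6-month results. The named primary analyses in Section 9.5 cover safety through Day 85 (Cohorts 1a and 3) or 28 days after dose 2 (Cohort 2). The gap concerns the end-of-study summary.
- That everything Amendment 14 added ends in a listing. Its immunogenicity data are not censored at unblinding.

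Figure 10, which sets out the strategy by scenario, was not available for this check.

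**Conclusion.** The contradiction is in the current text and concerns a primary endpoint. For participants unblinded under Amendment 10, following Sections 9.7.1, 9.7.2 and 9.8 gives no summary of SAEs and AESIs by vaccine group over the window in Section 3. A separate analysis plan that follows these sections would inherit the conflict.

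In Cohorts 1 and 3, at most about 33% of the post-dose-2 window is analysed if unblinding fell on the Amendment 10 date, and 64% if it fell as late as the Amendment 15 date. Both figures assume no first dose before 4 May 2020. In Cohort 2 the 6-month window is cut short on the protocol's own account of when unblinding occurs. The share of AESI time lost cannot be fixed: it may be most or all of it, depending on local dates that are not given. Participants in countries without local approval of Amendment 10, and not unblinded for another reason, are unaffected.

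**What to change.** Reconcile Sections 3, 6.6, 9.4.2, 9.7 and 9.8.

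- Keep censoring at unblinding for the blinded placebo comparison and for solicited and non-serious AEs.
- Add a descriptive table of SAEs and AESIs by original vaccine group, from first vaccination to the earliest of unscheduled vaccine, ad hoc booster, last contact or the Section 3 limit. Show follow-up time by group, because unblinding dates differ and the second year depends on consent. Split it at unblinding and label the later part open-label.
- Show AESI follow-up from local approval of Amendment 11, and present retrospectively identified thrombosis and thrombocytopenia events separately.
- Replace the route from Section 6.6 through 9.6 to 9.7 with a statement of what is analysed after unblinding.

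The cost is wording and a few tables from data already collected. The downside is that rates after unblinding are open-label and cannot be read as a blinded comparison; the split and label deal with that.
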